The Effect of Administering the Probiotic *Lactiplantibacillus plantarum* DAD-13 on Procalcitonin Levels, C-Reactive Protein, and Interleukin-6 in Sepsis Patients in the ICU of H. Adam Malik Hospital, Medan

NCT Number: Pending

Document Date: July 9, 2025

Study Protocol

Title: The Effect of Administering the Probiotic *Lactiplantibacillus plantarum* DAD-13 on Procalcitonin Levels, C-Reactive Protein, and Interleukin-6 in Sepsis Patients in the ICU of H. Adam Malik Hospital, Medan

NCT Number: Pending

Document Date: July 9, 2025

Background and Rationale: Sepsis is a life-threatening organ dysfunction caused by a dysregulated host response to infection. Dysbiosis and disruption of intestinal barrier function are critical components of sepsis pathophysiology. Probiotics may modulate inflammatory responses and restore gut microbiota balance. *L. plantarum* DAD-13, an Indonesian probiotic strain, has demonstrated immunomodulatory potential in preclinical studies. This study aims to evaluate the effect of *L. plantarum* DAD-13 on inflammatory markers and gastrointestinal outcomes in ICU patients with sepsis.

Study Objectives: Primary Objective:

- To assess the effect of *L. plantarum* DAD-13 on Procalcitonin (PCT), C-Reactive Protein (CRP), and Interleukin-6 (IL-6) levels.

Secondary Objective:

- To assess changes in defecation frequency and stool consistency.

Study Design:

- Type: Prospective, randomized, double-blind, placebo-controlled trial
- Sample size: 30 patients (15 per group)
- Duration: 4-day intervention period

Eligibility Criteria: Inclusion:

- Age 18–65 years
- Diagnosed with sepsis
- Admitted to ICU
- Receiving enteral nutrition

Exclusion:

- Known gastrointestinal disease
- Immunocompromised status
- Probiotic allergy
- Use of other probiotic products

Intervention:

- Experimental Group: 2 capsules/day of L. plantarum DAD-13 (Vipilac®)
- Control Group: 2 capsules/day of placebo (maltodextrin)
- Duration: 4 days

Endpoints:

- Primary: Change in serum PCT, CRP, and IL-6 from baseline to day 4
- Secondary: Frequency and consistency of defecation

Data Collection and Monitoring:

- Biomarkers (PCT, CRP, IL-6) measured at T0 (day 1) and T1 (day 4)
- Stool data collected daily
- Double-blind protocol maintained throughout study

Ethics: Approved by the Health Research Ethics Committee of Universitas Sumatera Utara. Informed consent obtained from all participants or legal representatives.

Statistical Analysis Plan (SAP)

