Study Population:

- Intent-to-Treat (ITT): All randomized participants
- Per-Protocol (PP): Participants who completed the 4-day intervention

Descriptive Analysis:

- Means and standard deviations (SD) for continuous variables
- Frequencies and percentages for categorical variables

Comparative Analysis:

- Within-group (T0 vs T1): Wilcoxon Signed Rank Test (non-parametric)
- Between-group: Mann-Whitney U Test for biomarkers, Chi-square for defecation frequency/consistency
- Significance level: $p < 0.05$

Missing Data:

- Data imputed using last observation carried forward (LOCF) method for missing T1 values

Informed Consent Form (ICF)

Study Title: The Effect of Administering the Probiotic Lactiplantibacillus plantarum DAD-13 on PCT, CRP, and IL-6 in Sepsis Patients

Investigator: [name] [name] **Institution:** H. Adam Malik Hospital, Universitas Sumatera Utara **Contact:** [contact], [name]

Purpose: You are invited to participate in a clinical study evaluating the effects of a probiotic on inflammation and gut function in sepsis patients. Participation is voluntary.

Procedures:

- You will receive either probiotic capsules or placebo for 4 days
- Blood samples will be taken twice (day 1 and day 4)
- Stool consistency and frequency will be recorded

Risks and Benefits:

- Risks: Mild gastrointestinal discomfort, rare allergic reaction
- Benefits: Possible improvement in inflammation and gut function

Confidentiality: All data will be anonymized. Your name will not appear in any publication.

Voluntary Participation: You may withdraw from the study at any time without affecting your medical care.

Consent: By signing this form, you agree to participate in this study.

Participant Name: _____ Date: _____ Signature: _____

Witness Name: _____ Signature: _____

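### The consent form's risk list does not address infection by the study organism, and no listed data item would record such an infection as harm

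*Protocol*

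**What the plan says.** Under Background and Rationale, the protocol describes the condition of the study population in these terms: "Dysbiosis and disruption of intestinal barrier function are critical components of sepsis pathophysiology". Its stated aim concerns inflammatory markers and "gastrointestinal outcomes in ICU patients with sepsis". Under Intervention, the experimental group takes two capsules a day of the named *L. plantarum* strain for four days and the control group takes maltodextrin capsules. Eligibility requires that patients be in the ICU with sepsis and on enteral nutrition.

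The Informed Consent Form is reproduced from its title to its signature lines. Its entire statement of risk is "Risks: Mild gastrointestinal discomfort, rare allergic reaction".

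The endpoints are "Primary: Change in serum PCT, CRP, and IL-6 from baseline to day 4" and "Secondary: Frequency and consistency of defecation". Data Collection and Monitoring has three entries: the three biomarkers on days 1 and 4, stool data each day, and maintenance of the blind.

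**The concern.** The protocol uses the damaged gut barrier to explain why a probiotic might help. The same fact bears on what a bacterial product might do in these patients, but the consent form does not carry it over. A patient or legal representative reading the form would not learn that infection with the administered organism is a possibility.

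Two things are at stake. Consent would be given on a risk list that leaves out a possibility raised by the protocol's own reasoning. And if such an infection occurred, the trial as written has no place to record it, so it would pass as part of the underlying sepsis and would not appear as a possible harm of the product.

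**Working it through.** No arithmetic decides this point. The check is to set the relevant parts of the document side by side.

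**Step 1. What the rationale implies.** The protocol makes three separate statements: the product is a bacterial strain (Intervention), the patients have sepsis and are in the ICU (Eligibility Criteria), and barrier disruption is central to sepsis (Background and Rationale). The protocol does not join them into a statement that the organism may cross the gut wall. That link is an inference, but it needs no premise beyond these three.

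**Step 2. What is disclosed.** The consent form names two risks, one confined to gut symptoms and one allergic. Neither covers infection. Infection, bacteraemia or translocation by the study organism is not mentioned anywhere else in the protocol or the consent form.

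**Step 3. Whether anything would record it.**

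| Place | What is listed | Would it record infection by the study organism? |
|---|---|---|
| Endpoints, primary | Change in PCT, CRP and IL-6 | No. These markers do not identify an organism, and the patients enter with sepsis |
| Endpoints, secondary | Stool frequency and consistency | No |
| Data Collection and Monitoring | Biomarkers on two days, daily stool data, blinding | No. No adverse events and no culture results |
| Consent form, Procedures | Two blood samples, stool recording | No |
| Statistical Analysis Plan section | Comparisons of biomarkers and stool outcomes | No. No safety tabulation |

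No follow-up after day 4 is described, so an event appearing later would also fall outside the data.

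**Step 4. Who is affected.** The design has 15 patients per group. All 2 × 15 = 30 participants or their representatives consent on the same text, and the 15 in the probiotic group are exposed to the organism. The document gives no rate for such infections, so no expected number of events can be derived and none is assumed.

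**The case against.** The strongest reply is that nothing here is contradictory. The barrier statement supports an expected benefit, the protocol never says that the organism may reach the blood, and the documents contain no safety data on the strain. That stands as far as it goes: the document is silent on this risk, and does not state anything false about it. But the omission is visible from the protocol's own premises, and the consent form is the place where it should be dealt with.

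A second reply is that the missing adverse-event collection is a wider gap, of which this is a special case. That also stands. What is specific to this point is the consent line and the naming of the organism in whatever safety recording is added. Leaving the matter to a separate analysis plan would not answer it, since consent content and the choice of safety data to collect belong in the consent form and the protocol.

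Several stronger readings are tempting, and the documents do not support them:

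- **The exclusion as evidence.** A reader might take "Immunocompromised status" in the exclusion list as a sign that the sponsor feared infection. No reason is given, and with PCT, CRP and IL-6 as endpoints it fits equally well with avoiding confounded biomarkers. Another exclusion, use of other probiotics, also corresponds to no disclosed risk, so no pattern can be built on the list.
- **A ranking of risks.** A reader might call this the most serious risk of the trial. The documents supply no rate or severity data with which to rank it.
- **A numerical bound.** A reader might compute an upper confidence limit for zero events in 15 patients. That limit follows from the sample size for any unseen event, and the protocol claims nothing about infection rates. It does not bear on the consent wording.
- **An effect on the efficacy result.** A reader might infer that an infection would raise the three biomarkers and be read as lack of efficacy. The document does not show this. It would require an infection inside the day 1 to day 4 window large enough to alter the comparison, and the between-group test is a Mann-Whitney test, in which one extreme value among 15 has limited influence.

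**Conclusion.** The point holds as a gap in disclosure and recording. The consent form's risk list does not address infection by the study organism, although the rationale describes a damaged gut barrier in patients who are given bacteria, and the listed data collection would not record such an infection as harm. Its reach is the consent of all 30 participants and the exposure of 15; its frequency is unknown from these documents.

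The conclusion assumes that the consent form as reproduced is the complete form and that no separate safety procedure exists outside this protocol. It does not affect the validity of the biomarker comparison. It is a change that should be made because it improves patient information and safety recording at little cost.

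**What to change.** 1. **Consent form, Risks and Benefits.** Reconcile the risk line with the rationale: state that the product contains bacteria and that infection with the study organism, including bloodstream infection, is possible when the gut barrier is damaged.
2. **Protocol, Data Collection and Monitoring.** Add adverse-event recording that includes any Lactobacillus/Lactiplantibacillus isolate from cultures taken in routine care, over a follow-up window that the sponsor states. Report such isolates to the ethics committee and tabulate them by arm.
3. **State the limit of this record.** An isolate identified to genus flags a possible event. It does not by itself attribute the event to the study strain.

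The cost is an amendment through the ethics committee and one case-report field filled from the routine microbiology record. No extra cultures or procedures are needed. The downside is a less favourable risk statement, which may lead a few families to decline.
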